Number of Participants with Rationale	The power analysis was informed by a precedent human study (PMID: 36615694) that established average leucine AUC values to be 20,000 (with a standard deviation of 2,000) for plant-based drinks and 28,000 (with an updated standard deviation of 6,100) for animal-based drinks (whey). The mean difference between plant and animal drinks was identified as 8,000 units from this research. This study was performed in men and women, with no differences in leucine AUC between genders. Adjusting for the crossover design, the power analysis indicated that approximately 9-10 participants would suffice to achieve the desired statistical power of 0.80 and an alpha level of 0.05. This sample size estimation directly reflects the enhanced efficiency and reduced variability afforded by the crossover design, as compared to a traditional parallel-group RCT, in discerning significant differences in leucine AUC among the dietary interventions examined. We will recruit 12 participants to account for dropouts (10-20%). Calculations have been done in python
Study Intervention	
Participants will be administered three different drinks in a randomized crossover order. These drinks are:
 
 
- Animal-based A: A commercially available high protein drink, based on animal proteins (Fresubin Protein Energy).
 
- Animal-based B: A homemade drink containing animal-based proteins, using a specific animal-based protein isolate mix.
 
- Plant-based A: A homemade drink containing plant-based proteins, formulated to have the same macronutrient content as the animal-based drinks.
 
 
Participants will arrive fasted at the lab. After a 60 min seated rest, a baseline blood sample will be taken 30 minutes prior to consuming the drink. After consuming the assigned drink, a blood sample will be collected 30, 60 and 90 minutes later, to determine leucine appearance (AUC). This procedure will be repeated three times, each with a different drink, with 5-7 days washout in between. The primary measure of the study is the leucine content in the blood, determined using High-Performance Liquid Chromatography (HPLC).

Control Intervention	Each participant acts as his/her own control. The usual inter-subject variability is minimized by the cross-over design as each participant is used as their internal control as each drink is tested in every participant.

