Study procedures	
 
- Recruitment and Screening (Month 1): Recruitment and screening aim to enroll 14 participants within one month.
 
- Lab Visits (Months 2-3): Participants undergo three lab visits of about 4 hours at Laboratory Exercise and Health, ETH Zurich. Patients arrive fasted at the lab. Each visit includes a 60-minute seated rest, followed by one blood sample collection before and two blood sample collections after drink consumption. Samples are processed and stored at -80°C for further analysis.
 
- Analysis (Month 4): High-Performance Liquid Chromatography (HPLC) used to measure leucine content in blood samples, assessing protein bioavailability.
 

Study Duration and Schedule	Planned 06/2024 of First-Participant-In Planned 09/2024 of Last-Participant-Out
Investigator(s)	[name] [name] Laboratory of Exercise and Health Department of Health Sciences and Technology ETH Zürich [name] [contact] [contact]
Study Center(s)	Laboratory Exercise and Health, ETH Zurich, [name]
Data privacy	Privacy of data is guaranteed. Unique identifiers will be assigned to participants. This means that the data collected, analyzed, and reported cannot be traced back to individual participants. Secure Data Storage: All data, both physical and electronic, is stored in secure, access-controlled environments. All data is stored in an encrypted digital system (REDCap). Biological material in this study is not identified by participant name but by a unique participant number. Biological material is appropriately stored in a restricted area only accessible to the authorized personnel.

	Access to data will be restricted to authorized personnel, and appropriate encryption techniques will be applied to protect participant confidentiality.

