#### 3.2 Primary endpoint

Primary endpoint: Leucine bioavailability in blood (HPLC), assessed by Area Under the Curve (AUC). We specifically chose leucine as this is the primary amino acids that triggers the synthesis of new proteins in the muscle via mechanistic target of rapamycin ([name] et al., 2020). Typically, when a protein source is rich in leucine and consumption of it leads to a high level of leucine in the blood after consumption, like with whey protein, it promotes more muscle protein synthesis compared to a drink based on a single plant protein source, such as soy. Therefore, with our new

drink, we aim to optimize the appearance of leucine in the blood, which is a good indicator of protein synthesis in resting muscles. Age does affect bioavailability and protein synthesis (Schiaffino et al., 2013), hence, for this pilot trial we opt to study young, healthy individuals, males and females.

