Participants will arrive fasted at the lab. After a 60 min seated rest, a baseline blood sample will be taken 30 minutes prior to consuming the drink. After consuming the assigned drink, a second, third and fourth blood sample will be collected 30, 60 and 90 minutes later, to determine leucine appearance (Area Under the Curve, AUC). This procedure will be repeated three times, each with a different drink, with 5-7 days washout in between. The primary measure of the study is the leucine content in the blood, determined using High-Performance Liquid Chromatography (HPLC), to assess the bioavailability of the proteins in the drinks.

We are testing two kinds of animal-based protein drinks and one plant-based protein drink. The reason for this is we are creating alternatives to the nutritional drinks currently sold by companies like Nestlé and Fresubin (FSMP products). We have made a drink using whey (which comes from animals) and another using a combination of pea and rice (which are plants), ensuring both have the same mix of nutrients as the ones you can buy now. We want to see if our drinks are better at delivering leucine to the body compared to the existing products.

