###### **2. Lab Visits (Months 2-3):**

Participants will undergo three lab visits at Laboratory Exercise and Health, D-HEST, [name]

- Participants will arrive fasted at the lab (no food and beverages starting at midnight)
- Each lab visit involves a 60-minute seated rest, followed by blood sample collection minutes before consuming the drink and 30, 60 and 90 minutes after consuming the assigned drink (see point 3. below).
- Three following three different drinks will be administered in a randomized order, with 5-7 days washout between visits:
  - Animal-based A: A commercially available high protein drink, based on animal proteins (Fresubin Protein Energy).
  - Animal-based B: A homemade drink containing animal-based proteins
  - Plant-based B: A homemade drink containing plant-based proteins, formulated to have the same macronutrient content as the animal-based drinks.
- All ingredients of the drink are food grade and prepared at a food-grade level (Laboratory of Sustainable Food Processing, ETH Zurich). Exact ingredients are: Plant protein isolates (pea, rice, hemp, pumpkin), Animal-based isolates (whey) water, maltodextrin, fruit puree (raspberry). All ingredients are commercially available.
- Total volume of the drink will range from 250ml to 400ml depending on the bodyweight of the participant
- During the first visit there will be also a short assessment of participants' characteristics (i.e. sociodemographic data and self-reported physical activity level). The following characteristics will be collected by the project leader/study personnel, inserted in a dedicated electronic Case Report Form (eCRF) within a web-based Electronic Data Capture (REDCap) system.

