### **Expected Biases and Mitigation Measures:**

We acknowledge potential biases in the study, such as order effects and participant compliance. To mitigate these biases:

- Randomized order of drink administration minimizes order effects
- Drink administration is conducted in a single-blinded manner.
- Strict adherence to the washout period reduces carryover effects.
- Participants will receive thorough instructions and reminders to enhance compliance.

Table 1. Timeline of study procedures

Time (Months)	Month 1	Month 2-3			Month 4
Visit	Information	Lab visit 1	Lab visit 2	Lab visit 3	Analysis
Recruitment and screening	+				
Written consent	+				
Check inclusion-/exclusion criteria	+				
Participant Characteristics		+			
Questionnaire		+			
Sampling		+	+	+	
Assessment of primary endpoints					+

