## 5 STATISTICS AND METHODOLOGY

### 5.1. Statistical analysis plan and sample size calculation

Our null hypothesis posits that the consumption of our plant-based, food-grade beverage does not result in a statistically significant difference in blood leucine levels compared to the consumption of an animal-based drink currently available in the market (Resource, Nestlé). Specifically, we anticipate that the leucine level attained by our plant-based drink does not exceed 90% of the level achieved by the animal-based alternative.

The study employs a crossover randomized controlled trial (RCT) design to investigate differences in leucine absorption, as measured by Area Under the Curve (AUC), following the consumption of animal drink A, animal drink B, and plant drink C. Each participant serves as their own control, receiving each of the three treatments in a randomized sequence over separate periods.

Detailed statistical plan:

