# 7 FURTHER ASPECTS

## 7.1 Overall ethical considerations

The scientific value of this study lies in its evaluation of the bioavailability of leucine from a plant-based protein drink as compared to an animal-based one. This research is particularly relevant in the field of nutrition science, as it addresses the challenge of developing sustainable, plant-based protein sources that are nutritionally comparable to animal proteins. The study contributes significantly to the understanding of how plant-based diets can be optimized for enhanced human health, aligning with sustainability objectives in food production.

Our team has formulated a plant-based drink that, based on preliminary data and specific formulations using a variety of plant sources, is expected to increase the bioavailability of leucine compared to drinks made from a single plant protein source. This aspect is crucial as it opens the possibility of creating plant-based protein options that are not only environmentally sustainable but also nutritionally effective.

Currently, there is a gap in knowledge regarding how a beverage specifically optimized for amino acid bioavailability, particularly leucine, stacks up against traditional animal-based protein drinks. This study aims to fill that gap, providing valuable insights into the potential of plant-based proteins in meeting nutritional needs.

**Justification of Methodology:** High-Performance Liquid Chromatography (HPLC) has been selected for its accuracy in measuring specific amino acids, such as leucine, in blood samples. This method is known for its precision, making it ideal for quantifying amino acid levels accurately. The use of a randomized crossover design in this study ensures that each participant serves as their own control. This approach significantly enhances the reliability of the results, as it reduces the variability that can arise from individual differences between participants. Standard procedures like fasting and routine blood sampling are incorporated to accurately assess the bioavailability of nutrients. Fasting ensures that the baseline levels of amino acids are consistent across participants, while routine blood sampling allows for the tracking of changes in leucine levels over time following the consumption of the test drinks.

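### Fasting is defined only by a midnight cut-off, so fasting length and evening intake can differ between one participant's three visits and add avoidable within-person noise

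*Combined protocol and SAP*

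**What the plan says.** Section 4.3 (Lab Visits) sets the rule: "Participants will arrive fasted at the lab (no food and beverages starting at midnight". The synopsis and section 3.4 say only that participants arrive fasted.

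All other timing is relative to arrival or to the drink. The synopsis and section 3.4 state: "After a 60 min seated rest, a baseline blood sample will be taken 30 minutes prior to consuming the drink". Three further samples follow at 30, 60 and 90 minutes. On visit length the synopsis says: "Participants undergo three lab visits of about 4 hours at Laboratory Exercise and Health, ETH Zurich". On spacing, section 3.4 says: "This procedure will be repeated three times, each with a different drink, with 5-7 days washout in between".

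The synopsis (Ethical consideration) and section 7.1 give fasting a specific job: "Fasting ensures that the baseline levels of amino acids are consistent across participants". Section 5.1 makes the drink comparison a within-person one: "Each participant serves as their own control, receiving each of the three treatments in a randomized sequence over separate periods". The primary endpoint in section 3.2 is leucine AUC, with no statement on whether it is total or baseline-corrected.

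Section 4.1 restricts caffeine and high-intensity exercise before participation. The bias list in section 4.3 names randomised order, single blinding, the washout and this: "Participants will receive thorough instructions and reminders to enhance compliance". It does not mention fasting length, time of day or the previous evening's food.

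**The concern.** A midnight cut-off sets the latest time to stop eating. It does not set how long a person has fasted when blood is drawn. That depends also on when the visit starts and when the last meal was, and the plan leaves both open. One participant could comply with the rule at all three visits and still arrive with quite different fasts, or with a late protein-rich snack before one visit and an early light supper before another.

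In a crossover, a participant's visits should differ as little as possible except in the drink. Visit-to-visit differences in the fasting state go into the within-person error against which the drinks are compared. They cannot be standardised after sampling and, with last intake unrecorded, could not be examined either. The background section says the pilot is meant to refine methods and to set the size of a larger trial, so avoidable noise would also enter the variance estimate used for that.

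**Working it through.** **1. The plan's own figure.** The point disputes no stated number. For context, the code in section 5.1 reproduces: d = 8,000/6,100 = 1.311; f = √(d²/(1+d²)) = 0.795; the ANOVA power routine with 3 groups, alpha 0.05 and power 0.80 gives 18.59; 18.59/(1 + 2 × 0.5) = 9.29, the stated 9-10. This checks the arithmetic only, not whether the formula is valid.

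**2. What is controlled.** From the synopsis and sections 3.4, 4.1, 4.3 and 7.1:

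- Latest time of intake: fixed at midnight.
- Clock time of arrival, or a window for it: not given.
- Same start time for one participant's three visits: not required.
- Length of the fast in hours: not given.
- Evening meal or supplement: not controlled.
- Time of last intake: not recorded.

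The 5-7 day spacing adds to this. Visits 5 or 6 days apart fall on different weekdays, so a repeated time slot cannot be taken for granted.

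**3. Clock arithmetic.** The assumption is arrival between 07:00 and 12:00, with the baseline sample drawn straight after the 60-minute rest. The minimum fast at baseline is then the arrival hour plus 1:

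- 07:00 gives 8 h
- 08:00 gives 9 h
- 10:00 gives 11 h
- 12:00 gives 13 h

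The range is 13 − 8 = 5 h, a ratio of 13/8 = 1.6. These are minima. Someone who stopped eating at 19:00 adds 5 h to each.

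**4. Route to the endpoint.** If a different fasting state shifts leucine by δ throughout sampling, a total AUC from −30 to 90 minutes moves by 120 × δ. An incremental AUC removes that shift, but not a change in the response to the drink. The plan does not say which AUC it uses, and it gives no relation between fasting length and leucine, so δ cannot be supplied.

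**5. Illustration of scale.** Take the plan's SDs (2,000 and 6,100) and correlation (0.5), and add a hypothetical visit-to-visit SD of e AUC units. The SD of a paired difference is √(2,000² + 6,100² − 2 × 0.5 × 2,000 × 6,100 + 2e²). Power is for an unadjusted two-sided paired t-test of an 8,000 difference with 10 participants:

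- e = 0: SD 5,386; power 0.986
- e = 1,000: SD 5,569 (3% larger); power 0.980
- e = 2,000: SD 6,084 (13% larger); power 0.958
- e = 3,000: SD 6,856 (27% larger); power 0.906

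No value of e is supported by the documents. The list shows only how noise of a given size would act. A smaller true difference would be more sensitive to it.

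**The case against.** The strongest reply is that no effect has been shown. The documents nowhere link fasting length or time of day to leucine, and the hours used above are assumed. That stands, and it is why no AUC figure is claimed. The plan itself, however, treats fasting as what makes baseline values consistent, so it is reasonable to ask that the fast be comparable between visits.

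A reader might infer that 36 visits of about 4 hours force several start times a day. The documents do not support this. The visits (12 × 3 = 36) are spread over months 2-3. With 40-44 working days (five-day weeks assumed) that is 36/44 = 0.8 to 36/40 = 0.9 per day. Even the enrolment goal of 14 in section 4.3 gives 42 visits, about one per day. A single daily start time is feasible; it is just not required.

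A reader might also infer that the rule contradicts the plan's stated claim about visits. That claim concerns consistency across participants. The step to one participant's three visits follows from the crossover, not from the plan's words. Matching visits within participant would still let two participants have different usual start times, which matters less for a within-person contrast.

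It is also fair that a baseline sample at every visit makes baseline differences visible, that caffeine and exercise are already restricted, and that this is a pilot. These points lower the severity. They do not close the gap.

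**Conclusion.** The point holds as a minor gap in standardisation. The fasting rule leaves fasting length and evening intake free to vary between one participant's visits, and nothing else in the plan limits or records that variation. Under the assumed 07:00 to 12:00 arrivals, the minimum fast at baseline runs from about 8 to 13 h. The effect on leucine AUC cannot be computed from the documents.

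A reader might go further and infer a biased drink comparison. The documents do not support that: drink order is randomised, so differences in fasting should fall on the drinks by chance. Chance imbalance is possible with 12 people, but the expected cost is precision. No stated figure changes.

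**What to change.** In section 4.3 (Lab Visits), add three requirements:

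- Each participant's three visits start at the same clock time, for example within 1 hour of visit 1.
- Participants repeat the same evening meal at about the same time before each visit, and take no protein or amino-acid supplement afterwards.
- The time of last intake is recorded in the eCRF at each visit.

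The first two belong together. Equal start times alone do not equalise the fast, because midnight is only the latest stopping time. The third lets compliance be checked.

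The cost is protocol wording, one eCRF field per visit, less flexible booking, and the small burden on participants of matching three evening meals. Sample size, drinks and sampling times are unchanged.

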### **Procedure routine blood sample collection**

Blood Sample Collection: Venous blood samples will be taken by a registered nurse during the 3 lab visits at four time points - 30 minutes before consumption of the drink, 30 minutes, 60 minutes and 90 minutes after the consumption of each drink. Blood will be drawn from the participant using a catheter. The selected vein, in the arm, will be disinfected with an alcohol swab. A catheter will then be inserted into the vein, and blood will be collected into appropriate tubes. After the blood collection, the catheter will be removed, and pressure will be applied to the puncture site with gauze or a cotton ball. The site will then be covered with an adhesive bandage or tape. All procedures will be performed following standard infection control protocols.

Throughout the whole protocol each day, approximately 30 ml of blood will be drawn (3 x 10 ml).

Processing and Storage: Blood will be centrifuged to separate plasma, and the samples are stored in -80 until further analysis.

### **3. Analysis (Month 4):**

High-Performance Liquid Chromatography (HPLC): The primary measure of the study is the leucine content in the blood. This method ensures precise assessment of protein bioavailability in the administered drinks. This is a method used for separating, identifying, and quantifying each component in a mixture. In our study, HPLC will be used to analyze the leucine content in blood samples. It is a precise method that allows for the effective measurement of specific amino acids like leucine. We will only measure leucine from the blood.

### **Expected Biases and Mitigation Measures:**

We acknowledge potential biases in the study, such as order effects and participant compliance. To mitigate these biases:

- Randomized order of drink administration minimizes order effects
- Drink administration is conducted in a single-blinded manner.
- Strict adherence to the washout period reduces carryover effects.
- Participants will receive thorough instructions and reminders to enhance compliance.

Table 1. Timeline of study procedures

Time (Months)	Month 1	Month 2-3			Month 4
Visit	Information	Lab visit 1	Lab visit 2	Lab visit 3	Analysis
Recruitment and screening	+				
Written consent	+				
Check inclusion-/exclusion criteria	+				
Participant Characteristics		+			
Questionnaire		+			
Sampling		+	+	+	
Assessment of primary endpoints					+

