### 3.3 Study design

This will be an exploratory, single center, randomized, single-blinded, cross-over controlled pilot study with three arms: animal-based A, animal-based B, plant-based A. This study is designated as a 'pilot' because its objective is to generate scientifically valid data that can be leveraged for a more extensive future study focusing on older individuals experiencing malnutrition.

This trial design has the highest scientific validity as each participant will serve as their own control, and randomization determines the order in which the participants receive the drinks. The usual inter-subject variability is minimized by the cross-over design as each participant is used as their internal control as each drink is tested in every participant.

This study is a preliminary step (pilot) where we will examine how well leucine from various protein drinks is absorbed by people younger than 40 years old, as detailed in section 3.4. The findings from this initial study will help us design and carry out a more extensive, main study with older participants.

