## 4 STUDY POPULATION AND STUDY PROCEDURES

### 4.1 Inclusion and exclusion criteria, justification of study population

A total of 12 healthy volunteers will be recruited for this study of which 6 males and 6 females.

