##### **Sequence of Planned Procedures:**

###### **1. Recruitment and screening (Month 1)**

Recruitment and screening are projected to span one month, with the goal of enrolling 14 study participants.

- Participants will be recruited through advertisements and social media.
- Screening procedures will ensure eligibility criteria are met.

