#### 2. ANOVA

Our analysis will feature an ANOVA to examine the main effects of each drink (factors A, B, and C) and their interaction effects. This involves calculating sums of squares, degrees of freedom, mean squares, and F-statistics to understand each factor's impact and the interactions among them. We will interpret these effects, reporting the overall F-statistic and its associated p-value, and use a significance level to declare statistical significance.

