## 5.2. Handling of missing data and drop-outs

Missing data will be handled by complete case analysis. If the participant withdraws prematurely or drops out (i.e. before Lab visit 3), they will be replaced by recruitment of new subjects to ensure an adequate number of participants in the study.

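### The plan relies on random drink order but does not say the six orders will be balanced; if orders are drawn independently for 12 people, drink and visit will almost never balance, a modest loss that a balanced list avoids at no cost

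*Combined protocol and SAP*

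**What the plan says.** Section 3.3 describes a "cross-over controlled pilot study with three arms: animal-based A, animal-based B, plant-based A" and says that "randomization determines the order in which the participants receive the drinks". Section 5.1 has each participant "receiving each of the three treatments in a randomized sequence over separate periods". The synopsis, section 3.4 and the lab-visit text of section 4.3 likewise say only that the order is randomised. None of them mentions a list, blocks, a Latin square or equal use of the orders.

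Under Expected Biases and Mitigation Measures, section 4.3 names order effects as a possible bias. The remedy is "Randomized order of drink administration minimizes order effects".

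The planned model is given in section 5.1, item 2: "Our analysis will feature an ANOVA to examine the main effects of each drink (factors A, B, and C) and their interaction effects". It names no period or sequence term.

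On numbers, section 4.1 states "A total of 12 healthy volunteers will be recruited for this study of which 6 males and 6 females", and section 5.1 also recruits 12. The recruitment step in section 4.3 runs "with the goal of enrolling 14 study participants", and the synopsis repeats 14. Under section 5.2, people who leave before the third visit are analysed by complete case and "they will be replaced by recruitment of new subjects to ensure an adequate number of participants in the study". Whether a replacement inherits the leaver's order is not stated.

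**The concern.** Randomising the order makes order effects cancel on average over repeated trials. It does not minimise them in one trial of 12 people; equal use of the orders does. If, by chance, the plant drink falls more often at a late visit than an animal drink, drink and visit are correlated. The consequence depends on the model. With a visit term, the correlation inflates the variance of the drink contrast. Without one, any true visit effect enters that contrast directly. Neither can be rebalanced once the visits have taken place. Three drinks give six orders and 12 is twice six, so full balance is available at no cost to participants.

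**Working it through.** **Inputs.** Three drinks and three visits give 3! = 6 orders (sections 3.3 and 5.1). There are 12 participants (sections 4.1 and 5.1). AUC means are 20,000 (SD 2,000) for plant and 28,000 (SD 6,100) for animal drinks, with within-subject correlation 0.5 (section 5.1). Two inputs are my assumptions: each person draws one of the six orders independently with probability 1/6, and, in step 4 only, a linear drift from visit to visit.

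**1. The plan's own sample size.** I follow the printed code without endorsing it. The effect size is 8,000/6,100 = 1.311, so f = √(1.311²/(1 + 1.311²)) = 0.795. The solver returns 18.59, and 18.59/(1 + 2 × 0.5) = 9.29, which gives the stated 9-10. For dropout, 9/(1 − 0.20) = 11.25 and 10/(1 − 0.10) = 11.1, both rounding up to 12. The reserve is therefore 2 to 3 people.

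**2. How often independent draws balance.**
- Each order exactly twice: 12!/(2!⁶ × 6¹²) = 0.34%.
- Each drink exactly four times at each visit, by enumerating all allocations: 0.55%.

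The second is the condition that matters for efficiency.

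**3. Cost when the model has a visit term.** In a model with participant, visit and drink, the information on drinks is N(I − J/3) − D′D/N. Here I is the 3 × 3 identity, J the 3 × 3 matrix of ones, and D the drink-by-visit counts minus N/3. Balance means D = 0 and full efficiency. Exact enumeration for N = 12 gives:
- mean efficiency for one drink contrast 0.913, so 12 × (1 − 0.9129) = 1.05 participants lost;
- mean variance ratio 1.11;
- median efficiency 0.937, a variance ratio of 1/0.937 = 1.07;
- 5th percentile of efficiency 0.739, a variance ratio of 1/0.739 = 1.35;
- chance of losing at least one participant's information 44%, at least two 15%.

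**4. Cost when the model has no visit term.** Over the six orders, the visit number of the plant drink minus that of one animal drink takes the values ±1 (twice each) and ±2 (once each). Its mean is 0 and its variance (4 × 1 + 2 × 4)/6 = 2. The mean over 12 people has SD √(2/12) = 0.408 visits.

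For comparison, the SD of a within-person plant-animal difference is √(2,000² + 6,100² − 2 × 0.5 × 2,000 × 6,100) = 5,386. Its standard error at n = 12 is 5,386/√12 = 1,555.

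| Assumed drift per visit | Added error SD | Combined SE | Increase |
|---|---|---|---|
| 2% of 28,000 = 560 | 0.408 × 560 = 229 | √(1,555² + 229²) = 1,572 | 1% |
| 5% of 28,000 = 1,400 | 0.408 × 1,400 = 571 | √(1,555² + 571²) = 1,657 | 6.5% |

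The documents give no drift figure, so the table shows only how the error scales.

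**5. Does balance survive dropout?** In simulation, a balanced list of 12 that loses 2 or 3 people at random without replacement loses a further 0.18 or 0.28 of a participant through imbalance. Independent draws for 10 or 9 people lose about 1.06. If each replacement takes the leaver's order, the list is fully restored.

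**The case against.** The best reply is that silence is not a defect: a randomised sequence is compatible with a balanced list, and the sponsor may intend one. That stands. A reader might infer that allocation is unrestricted, but the documents do not say so. The calculations show what follows if it is.

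Five other stronger readings also fail.
- *The plan as written wastes a participant.* That loss needs a visit term, which section 5.1 does not name. Without it the cost is the one in step 4.
- *Unused orders are harmful.* Under independent draws at least one order goes unused in 56% of allocations, but three Latin-square orders used four times each also give D = 0 and a variance ratio of 1.00.
- *Replacements make matters worse.* Replacing one independent draw by another leaves 12 independent draws and the same distribution. The replacement rule matters only once a balanced list exists, or if dropout depends on order.
- *Orders must be balanced within sex.* Each person is their own control, so the effect of sex cancels from the drink contrast. Section 5.1 also reports no gender difference in the precedent study.
- *Drift will seriously distort the result.* The 5% is assumed. Visits are 5-7 days apart, samples are frozen and HPLC is run in Month 4, so season and visit-by-visit assay drift are weak explanations. Over randomisations the effect is extra variance, not systematic bias, and sampling error is larger.

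The trial is also an exploratory pilot with a small reserve and replacement of leavers, which argues for low severity.

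**Conclusion.** The point holds as an unspecified allocation method with a cheap remedy, not as a demonstrated imbalance. If orders are drawn independently, drink and visit will almost certainly be unbalanced. With a period-adjusted analysis, the average price is about one participant of 12, or a third to a half of the plan's reserve of 2 to 3. With the ANOVA as written, the price is whatever visit effect exists: about 1% to 6.5% on the standard error for drifts of 2% to 5% per visit. These sizes rest on independent equal-probability draws, 12 completers and, for the last figures, the plan's SDs and correlation. Severity is low, but the order cannot be corrected after the visits, so it should be settled before the first one.

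**What to change.** In sections 3.4 and 4.3, state: *Drink orders are taken from a list prepared before the first visit, in which each of the six possible orders is used twice among the 12 participants. A replacement receives the order of the person replaced.*

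In section 5.1, add period to the ANOVA alongside participant and drink. Balance alone keeps visit effects out of the drink means but leaves them in the residual, so the list and the term belong together. With 36 observations the term takes residual degrees of freedom from 36 − 1 − 11 − 2 = 22 to 20.

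Reconcile 12 (sections 4.1 and 5.1) with 14 (synopsis and section 4.3). Fourteen is not a multiple of six, so the list does not fit until the planned number is settled; if 14 is meant to include reserves, say that they serve only as replacements. Balancing within sex is optional: six men and six women would allow each order once per sex.

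The cost is a few sentences and a 12-line list, with no added burden on participants.
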